### **Randomization**

Participants meeting the inclusion criteria were randomly assigned to one of the three groups following eligibility screening.

### **Intervention**

The study included two interventions ([name]'s PBI adapted for MADD; Surgeon General materials) and an active control (HPV materials). *The PBI*: The first section provides an introduction to the problem of underage drinking, DUI, and RWDD. It provides parents with an overview of the problems, various basic facts, instructions on how to use the materials, and comments from parents about the consequences associated with underage drinking. It also helps motivate parents to talk with their teen by emphasizing that such discussions could make a difference in both improving their relationship and reducing their teen's risk. The next two sections focus on developmental changes, relationship building, specific strategies that parents

can use to improve communication channels with their teen, and parenting types. The final section is an in-depth discussion of the risks of underage drinking, DUI, RWDD, and all of the major variables in the proposed theoretical network. Parental reluctance to engage in discussions is also considered. Discussion is provided of whom is most at risk, making agreements, specific strategies for talking so that teens listen, decision making, peer influences, and positive and negative reasons why some teens drink. This section also addresses the issues of alternatives to drinking, DUI, and RWDD, issues for discussion, and additional resources. Parents who were randomized to this group, received a link following the baseline assessment to access the materials. *The Surgeon General*: These materials provided parents information on how to prevent and reduce underage drinking, with sections defining what a drink is, why underage drinking is a problem, the results of underage drinking, what families can do about underage alcohol use, etc. *The Active Control (HPV materials)* provided information regarding the HPV vaccination.

### **Measures**

Data were collected online at baseline, 6-month, and 12-month for both parents and teens. Teens also had a 1-month follow-up. Ipsos provided demographic information on the parents based on panel demographics. Other measures included: DUI, riding with drinking drivers; alcohol use; intentions/willingness/attitudes/beliefs/norms to drink/DUI/RWDD; parental monitoring, permissiveness, modeling; intervention fidelity (Chen et al., 2008; Hultgren et al., 2015; Kann et al., 2014; Poulin et al., 2007; Abar et al., 2014; Mallett et al., 2011; Cartwright & Asbridge, 2011; Dhami et al., 2011; Collins et al., 1985; Dimeff et al., 1999; Marlatt et al., 1998; [name] & Jaccard, 1992; Grube & Voas, 1996; Beck & Treiman, 1996; Abar et al., 2009).

### **Primary Outcome Measure**

The primary outcome measures were typical weekend drinking, and declining to ride with impaired drivers.

### **Secondary Outcome Measures**

The secondary outcome measure was willingness to ride in a car with an impaired driver.

### **Intervention Variables**

Parents in the MADD and SG groups received a fidelity questionnaire to measure the useful, interesting, readable the sections of the intervention were.

### **Statistical Analysis Plan**

Statistical analyses were performed using IBM SPSS Statistics version 28. Each primary and secondary outcome was examined using Tukey's critical difference value to compare the means following Wilkinson et al., (1999) recommendations. This approach has been shown to have the most power and least Type I error rates with varying sample sizes to compare mean differences between conditions.

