## **Study Design**

A randomized 3-arm intervention (PBI, Surgeon General, Active Control) with 3 waves of online survey data collection for parents (baseline, 6-month, 12-month), and 4 waves for teens (baseline, 1-month, 6-month, 12-month).

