### **Sample Size, Power, and Attrition**

*Sample Size/Statistical Power*: The sample sizes were chosen based on statistical analytic and theoretical considerations. For example, for Aim 1 examining efficacy of the PBI, we aimed to have final dyad sample Ns of 588 and 532 (and approximately equal n's for our PBIs and control groups of 294 and 266) at the 6 and 12 month follow-ups, respectively. Using power estimation procedures described in Cohen (Cohen & Cohen, 1983) these sample sizes will yield power of greater than 0.80 for small effect sizes (e.g., 5-10%) in the MANCOVA-based analyses (omnibus tests, interactions, and planned comparisons). In our published papers with similar Ns comparing drinking for PBI and controls ([name] et al., 2013; Doumas et al., 2013; Ichiyama et al., 2009; [name] et al., 2009; Testa et al., 2010; [name] et al., 2001; [name] et al., 2004) we have detected effect sizes of .05 to .09 for main effects and .05 to .08 for interactions. Thus, with our final Ns we should have sufficient power to evaluate Aim 1.

*Attrition*: We will first examine if the attrition is random by forming a dummy variable that indicates completion or drop-out at each assessment. The dummy variable will be correlated with key variables in the study (e.g., Group, drinking/DUI/RWDD outcomes). In the past, we have observed nonsignificant correlations suggesting that the attrition has been random and then used the most advanced multiple imputation techniques to impute missing data. We then analyze all cases with the imputed data ([name] et al., 2009). Although we have not observed differential attrition by condition in our previous work, we recognize the potential. We will reduce this possibility by providing the controls with an online link to the intervention at the completion of the 12-month assessment. Thus, all conditions will be identical except for the timing of intervention. However, if we should observe non-trivial correlations (e.g., > .2) between the dummy variable reflecting completers vs. drop-outs, we will include the dummy coded variable as a covariate in subsequent analyses and attempt to interpret significant effects.

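### The efficacy comparison never uses the baseline value of the outcome, so precision available at almost no cost is not secured

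*Combined protocol and SAP*

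**What the plan says.** The Statistical Analysis Plan section names the software, one method and a reason for it. The method is: "Each primary and secondary outcome was examined using Tukey's critical difference value to compare the means". The section mentions no model, covariate, baseline term, change score or follow-up time.

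The section on sample size, power and attrition claims its power "in the MANCOVA-based analyses (omnibus tests, interactions, and planned comparisons". It lists no covariates for those analyses. Its attrition paragraph names the only covariate in the document, an indicator of completion versus drop-out. If that indicator shows non-trivial correlations (above about .2), "we will include the dummy coded variable as a covariate in subsequent analyses".

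Baseline data exist. The Study Design section lists "4 waves for teens (baseline, 1-month, 6-month, 12-month", and the Measures section says: "Data were collected online at baseline, 6-month, and 12-month for both parents and teens". The constructs listed under Measures include "DUI, riding with drinking drivers; alcohol use; intentions/willingness/attitudes/beliefs/norms to drink/DUI/RWDD". These cover the subject matter of the primary outcomes ("The primary outcome measures were typical weekend drinking, and declining to ride with impaired drivers") and of the secondary one ("The secondary outcome measure was willingness to ride in a car with an impaired driver").

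**The concern.** Two sections describe the efficacy analysis and do not name the same one. MANCOVA implies covariates, but none is given; the analysis section then drops MANCOVA and compares means. Baseline adjustment is therefore unspecified rather than ruled out. An analyst who follows the analysis section literally would leave the baseline measurement unused.

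This does not bias a comparison of randomised arms. It has two costs:

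- Intervals for each pair of arms are wider than the collected data allow, and chance baseline differences stay in the estimates.
- With the model left open, adjusted or unadjusted results could be chosen after the data are seen.

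The drop-out indicator does not fill the gap. It is determined after randomisation, is used only conditionally, and is aimed at attrition. The planned multiple imputation also addresses missing data and not this adjustment.

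**Working it through.** **Inputs from the document.** Targets of 588 dyads at 6 months and 532 at 12 months, with group sizes of 294 and 266; power above 0.80 for effects of 5–10% (all from the sample-size section). Three arms of 390, 393 and 393, total 1,176 (Sample Characteristics).

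**Assumptions.** Two-sided familywise α of 0.05; outcome SD of 1; r = 0.3, 0.5 or 0.7; equal split of the targets over three arms, 588/3 = 196 and 532/3 ≈ 177. The document states none of these.

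**The plan's own figure.** The metric of the 5–10% is not defined. Read as variance explained, f² = 0.05/0.95 = 0.0526 and the noncentrality is f² × N. At N = 588 this is 30.9, with power 0.9998 for two groups and 0.9994 for the three-arm omnibus test. At N = 532 it is 28.0, with power 0.9996 and 0.9985. The claim of more than 0.80 holds on this reading.

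**Effect of baseline adjustment.** The variance of a difference in arm means is multiplied by about 1 − r²:

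- r = 0.3: 1 − 0.09 = 0.91
- r = 0.5: 1 − 0.25 = 0.75
- r = 0.7: 1 − 0.49 = 0.51

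**Interval half-width.** The three-arm Tukey critical value is q/√2 ≈ 2.35, and the half-width is 2.35 × √(2/n) × √(1 − r²). For n = 196 unadjusted: 2.35 × 0.1010 = 0.237 SD.

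| n per arm | Unadjusted | r = 0.3 | r = 0.5 | r = 0.7 |
|---|---|---|---|---|
| 196 (588/3) | 0.237 | 0.226 | 0.206 | 0.170 |
| 177 (532/3) | 0.250 | 0.238 | 0.216 | 0.178 |
| 294 (stated group size) | 0.194 | 0.185 | 0.168 | 0.138 |
| 266 (stated group size) | 0.204 | 0.194 | 0.176 | 0.145 |

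**Difference detectable with 80% power.** This is (2.35 + 0.842) × √(2/n) × √(1 − r²), in SD units:

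| n per arm | Unadjusted | r = 0.3 | r = 0.5 | r = 0.7 |
|---|---|---|---|---|
| 196 | 0.322 | 0.308 | 0.279 | 0.230 |
| 177 | 0.339 | 0.324 | 0.294 | 0.242 |
| 294 | 0.263 | 0.251 | 0.228 | 0.188 |
| 266 | 0.277 | 0.264 | 0.240 | 0.198 |

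At r = 0.5, 196 per arm does the work of 196/0.75 = 261.

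**Power of a pairwise Tukey comparison.** Five per cent of variance between two groups is d = 2 × √0.0526 = 0.459. Unadjusted power is then 0.986 at 196 per arm and 0.975 at 177, so little is left to gain. For a smaller effect, d = 0.283 (about 2% of variance, illustration only), power at 196 rises from 0.67 to 0.72, 0.81 and 0.94 for the three values of r. At 177 it rises from 0.62 to 0.67, 0.77 and 0.92. At the stated group sizes of 294 and 266 it is already 0.86 and 0.82 unadjusted.

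**Zero-heavy counts.** A simulation with about 70% zeros (assumed), 196 per arm and 6,000 replicates gave adjusted-to-unadjusted variance ratios of 0.92, 0.78 and 0.66 at r of about 0.29, 0.47 and 0.60. The 1 − r² values, before r was rounded, were 0.92, 0.78 and 0.63. The factor is approximate but close.

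**The case against.** The strongest reply is that the unadjusted comparison is valid and, on the natural reading of the effect size, amply powered, so this is a refinement. That is right as far as it goes: the loss is in precision alone. Several narrower points also have weight.

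- **The gain depends on an unknown r.** At r = 0.3 the half-width shrinks by under 5%. Low rates of drinking or risky riding at baseline, plausible at a mean age of 16.33, would reduce the gain. This stands, and is why a range is shown.
- **The stated group sizes are 294 and 266.** Against about 392 randomised per arm they imply 75% and 68% retention, which is plausible; the equal split implies 50% and 45%. But 294 × 2 = 588 and 266 × 2 = 532, so as per-arm numbers they do not fit those totals over three arms. Both sets are tabulated, and the proportional gain is the same.
- **Baseline items are not scheduled one by one.** Alcohol use and willingness are listed fairly directly. A baseline value for declining rides is inferred from the riding construct. This stands for that outcome.
- **MANCOVA may signal an intention to adjust.** Possibly, but no covariate is named and the analysis section does not carry MANCOVA forward.
- **The analysis section is in the past tense.** If results are known, prespecification can no longer be secured. This limits the status of an adjusted analysis but does not remove its value.
- **The simulation checked a variance ratio only.** Familywise error and coverage with robust standard errors were not tested. This stands.

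**Conclusion.** The concern holds. As written, the plan compares unadjusted means although the same surveys were given at baseline, and its two descriptions of the analysis disagree. The comparison is valid but less precise than it could be.

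On the assumed equal split, half-widths at 6 months would be narrower by about 5% at r = 0.3, 13% at r = 0.5 and 29% at r = 0.7 (1 − √0.91, 1 − √0.75 and 1 − √0.51). The same percentages apply at 12 months and at the plan's stated group sizes. The size rests on r, which the document does not give. The stated power is met without adjustment if 5% means variance explained, so the benefit is tighter intervals and a settled model. The change should be made, but the trial's validity does not depend on it.

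**What to change.** - For each outcome at each follow-up, fit a linear model of the outcome on arm and the baseline value of that outcome. Use robust standard errors, given the likely skew of drinking counts.
- Make Tukey-adjusted pairwise comparisons of the adjusted means. If the software does not offer this with a covariate, apply the three-arm critical value (about 2.35 at these sizes) to the adjusted differences.
- Name the baseline item for each outcome, in particular for declining rides. Teen age and sex are optional further covariates.
- Keep the unadjusted Tukey table as supporting.
- Make the sample-size and analysis sections name the same analysis and list its covariates.
- If results are already known, label the adjusted analysis as not prespecified and show both sets.

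The cost is revised wording and a few lines of syntax. No new data are needed where the baseline item was collected, and missing baseline values can be handled by the multiple imputation already described.

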## **Objectives**

Three objectives for the research: 1) Evaluate the efficacy of the PBI (short and long term); 2) examine the mediators of the PBI that directly influence drinking, DUI, and RWDD behaviors; and 3) identify the moderators of intervention efficacy (the subgroups for whom the intervention is more vs less effective).

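### Objective 1 covers short- and long-term efficacy, but the analysis section names no wave, no baseline term and no contrast for change in the arm difference over time

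*Combined protocol and SAP*

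**What the plan says.** The first item under Objectives is to "Evaluate the efficacy of the PBI (short and long term"). Study Design gives "4 waves for teens (baseline, 1-month, 6-month, 12-month"), so each teen has a baseline and up to three follow-up measurements.

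The Statistical Analysis Plan section states a single method for every outcome, Tukey's "critical difference value to compare the means". Its stated purpose is "to compare mean differences between conditions". It mentions no wave, time factor, baseline covariate or model for repeated measurements. The outcome sections attach no time point either: "The primary outcome measures were typical weekend drinking, and declining to ride with impaired drivers".

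The section Sample Size, Power, and Attrition is worded differently. It gives target Ns "at the 6 and 12 month follow-ups, respectively", and bases power for Aim 1 on "MANCOVA-based analyses (omnibus tests, interactions, and planned comparisons"). It does not say that these interactions are group by time. Objective 3 concerns moderators, so they could equally be group by subgroup. The analysis section does not mention MANCOVA. The 1-month teen wave appears in no stated analysis and no power figure.

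**The concern.** A comparison of arm means has to be made at some wave, or on some average of waves, and the plan does not say which. If it is made separately at 6 and 12 months, the trial gets two verdicts and no estimate of how the arm difference moved between them. A result that is significant at 6 months and not at 12 invites the reading that the effect faded, yet a difference in significance is not a test of change. At stake is whether the report can say anything sound about durability, which a short- and long-term objective will lead readers to expect.

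A second, smaller cost is precision. The baseline outcome and the other follow-up waves are already collected and can sharpen the arm comparison, but the stated method uses neither.

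**Working it through.** **Plan's own figure.** The power section claims more than 0.80 for effects of 5–10% at N = 588 and 532. Reading 5% as variance explained, f² = 0.05/0.95 and noncentrality = N·f². At alpha 0.05 (assumed), power is 0.9998 and 0.9996 for two groups, and 0.9994 and 0.9985 for three. The claim is met on that reading. It concerns a group comparison at one wave and says nothing about change over time.

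**Inputs for the rest.**
- From the documents: 294 per group at 6 months and 266 at 12, totals 588 and 532, and 1,176 dyads in three arms (392 per arm on average).
- Three-arm follow-up counts are not stated, so two readings are used: 294/266 in every arm, or the totals split in three (588/3 = 196; 532/3 ≈ 177).
- Assumed: SD 1; the same true effect d at both waves; within-teen correlation ρ of 0.5 to 0.7; 12-month responders a subset of 6-month responders; Tukey critical value 2.344 for three arms.

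**Step 1: power at each wave.** Power = Φ(d/√(2/n) − 2.344). With d = 0.25:
- n = 294: Φ(3.031 − 2.344) = 0.75; n = 266: Φ(2.883 − 2.344) = 0.71.
- n = 196: Φ(2.475 − 2.344) = 0.55; n = 177: Φ(2.352 − 2.344) = 0.50.

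**Step 2: opposite verdicts under a constant effect.** The two estimates have correlation ρ√(n12/n6). P(discordant) = P6 + P12 − 2·P(both), with P(both) from the bivariate normal. For 294/266, d = 0.25 and ρ = 0.5, the correlation is 0.476 and P(both) is 0.589, so P(discordant) = 0.754 + 0.705 − 2(0.589) ≈ 0.28. Ranges below run from ρ = 0.7 to ρ = 0.5.

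| d (SD) | 294/266 per arm | 196/177 per arm |
|---|---|---|
| 0.25 | 22–28% | 27–34% |
| 0.30 | 13–16% | 23–29% |
| 0.40 | about 1.5% | 8–10% |

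At d = 0.25 and 294/266, the pattern of significance at 6 months only, which looks like fading, accounts for 14–17% of trials.

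**Step 3: 12-month contrast from a model on all follow-ups.** Take 392 per arm, monotone drop-out and compound symmetry. Retention is 85% at 1 month (assumed), 294/392 = 75% and 266/392 = 68%. Summing the inverse covariance over drop-out patterns and inverting gives a 12-month variance, relative to 12-month responders alone, of 0.942, 0.920 and 0.894 at ρ = 0.5, 0.6 and 0.7. That is 6–11% less variance, and power at 0.25 SD goes from 0.71 to 0.74–0.76.

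**Step 4: the change in effect.** In the same model the 12-minus-6-month change in the arm difference has SE 0.085, 0.076 and 0.066 SD. An unadjusted 95% interval is therefore ±1.96 × SE, about ±0.17 to ±0.13 SD. If every wave's count were a third smaller, these would widen by √1.5 = 1.22.

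**Step 5: baseline adjustment.** For a single wave the variance factor is 1 − ρ²: 0.91 at ρ = 0.3, 0.75 at 0.5 and 0.51 at 0.7. This does not simply add to step 3. Once baseline is in the model, the correlation left between follow-ups is ρ/(1 + ρ), which is 0.33 at ρ = 0.5, so later waves add less.

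**The case against.** The strongest reply is that Objective 1 asks for efficacy at short and long term, not for a test of decay. A randomised arm difference at 12 months is a long-term effect, and the power section gives Ns for both 6 and 12 months. This stands. A reader might infer that the trial cannot address persistence at all. The documents do not support that: per-wave comparisons are not excluded and would show whether an effect is present at 12 months. Nor do the documents themselves say that they will read a loss of significance as fading.

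Second, the power section does mention MANCOVA and interactions, so Tukey is not the only method in sight. This stands as evidence that two sections disagree. It does not close the gap, because neither defines a group-by-time term.

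Third, the attrition text describes multiple imputation and analysis of all cases. If the imputation model included the other waves, much of the 6–11% gain would already be recovered. The text partly reports past practice and does not list the imputation variables, so this cannot be settled.

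Fourth, a reader might infer a large power loss, from 0.71 to 0.85–0.88. Those higher figures belong to the average of the 6- and 12-month effects (27–33% less variance than 12-month responders alone). That is a different target, and it answers neither the short- nor the long-term question separately.

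Finally, frequent disagreement between waves depends on a small effect. If the plan's 5% is variance explained, d for two groups is 2√(0.05/0.95) ≈ 0.46, and discordance at 294/266 is about 0.2%.

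**Conclusion.** The gap is real but bounded. As written, the analysis section does not say which wave is tested, does not use the baseline outcome or the 1-month teen wave, and has no contrast for change in effect. The power section's MANCOVA neither supplies one nor is carried forward. Presence of an effect at 6 and at 12 months can be tested; a change between them cannot.

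The risk of a misleading pattern is material for effects near 0.25 SD, grows if arms are nearer 196/177 than 294/266, and becomes small by 0.40 SD at the larger counts. The efficiency argument is secondary: a few points of power at 12 months from the other follow-ups, and more from baseline adjustment if the correlation is 0.5 or higher. All of this rests on correlations, effect sizes and 1-month retention that the documents do not give, and on per-arm counts that they do not state for three arms. The change should be made, but its absence does not invalidate the randomised comparison at either wave.

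**What to change.** In the Statistical Analysis Plan section, for each outcome, specify one repeated-measures model on all teen follow-up waves: arm, wave, arm × wave, baseline outcome × wave, and unstructured within-teen covariance. The link should suit the outcome scale, which the documents do not give. From this model report:

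- the arm differences at 6 and at 12 months, with the Tukey adjustment;
- the 12-minus-6-month change in the arm difference, with its interval.

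State that any claim of persistence or decay rests only on the second item. If a 6/12-month average is also wanted, name it as a separate target. Align the power section with this model by saying which interactions it means and which per-arm counts apply to three arms. Say whether the imputation model includes the other waves.

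The cost is SAP wording and a standard procedure, with no new data; for a continuous outcome the named software's MIXED procedure is enough. The small downside is that a covariance structure must be specified, and unstructured is manageable with three waves at this sample size. The section is written in the past tense, so if results already exist the model should be labelled a supplementary analysis.

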### **Sample Characteristics**

Of those invited, 1,176 (28.5%) met the study eligibility criteria of being a parent or legal guardian to a 15-18 year old adolescent-teen and consented for both themselves and their teen to participate in the study. There were 562 (13.6%) participants who responded to the study invitation but did not meet the study eligibility criteria. Eligible dyads were randomly assigned to one of three conditions: Active Control (AC; n=390, 33.1%), Surgeon General (SG; n=393, 33.4%), or Mothers Against Drunk Drinking Parent-Based Intervention (MADD PBI; n=393, 33.4%).

At the T1 baseline survey, the average age of the teens was 16.33 (SD=1.09). About half of teens identified as female (49%) and most parents identified as female (54%). The majority of participants identified as White (78.2%), Black (8.7%), Asian (2.9%), Native Hawaiian or Pacific Islander (0.2%), American Indian or Alaska Native (1.2%), Multiracial (4.1%), Other (4%), and Hispanic (26.9%).

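### The reason given for choosing Tukey's test is false for three arms: a range step-down test holds the same family-wise error, keeps every Tukey rejection and recovers some power

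*Combined protocol and SAP*

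**What the plan says.** The design is "A randomized 3-arm intervention (PBI, Surgeon General, Active Control"), and the Sample Characteristics section reports 390, 393 and 393 dyads randomised to control, Surgeon General (SG) and PBI. There are thus three pairwise contrasts for each outcome at each time point.

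The Statistical Analysis Plan section names one inferential method: "Each primary and secondary outcome was examined using Tukey's critical difference value to compare the means". It defends the choice as follows: "This approach has been shown to have the most power and least Type I error rates with varying sample sizes". It names no competing methods, no alpha and no family of tests. The one source cited there for its recommendations is not in the bibliography.

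The Sample Size, Power, and Attrition section was written for a different analysis. It says "we aimed to have final dyad sample Ns of 588 and 532" at 6 and 12 months, with groups of 294 and 266, and that "these sample sizes will yield power of greater than 0.80 for small effect sizes", with 5-10% as the example. That claim is for MANCOVA-based analyses, including planned comparisons.

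**The concern.** The only inferential method in the plan rests on an optimality claim made without qualification. Single-step Tukey tests all three pairs against the three-group critical value, including pairs for which that much protection is not needed. If another procedure has the same maximum family-wise error and never loses a Tukey rejection, Tukey cannot have the most power. If other standard procedures make fewer false rejections, it cannot have the least Type I error either.

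What is at stake is power within one outcome at one time point, chiefly for the smaller contrasts. With two active arms, PBI against SG may well be one of these. Multiplicity across outcomes and time points is a separate matter that neither test addresses.

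**Working it through.** **Inputs.** From the documents: three arms; 390/393/393 randomised; planned final totals of 588 and 532; effect size of 5-10%; power above 0.80. Assumed, because the documents do not state them: two-sided 5% family-wise error per outcome and time point; normal means with common variance (SD 1); a standardised mean difference d.

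**1. The plan's own power figure.** Read 5% as variance explained: f² = 0.05/0.95 = 0.0526, with noncentrality N × f² = 30.9 (N = 588) or 28.0 (N = 532). The F test then has power 0.9998 (two groups) or 0.9994 (three groups) at 588, and 0.9996 or 0.9985 at 532. So the claim of more than 0.80 reproduces on this reading. It fails if 5-10% is read as Cohen's f (0.16 to 0.68). The group sizes are a two-way split: 588/2 = 294 and 532/2 = 266. Three arms give 588/3 = 196 and 532/3, about 177.

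**2. Critical values.** Tukey: q(0.05; 3, df)/√2 = 2.347 (N = 1,176) to 2.350 (N = 532), a per-comparison level of 0.0191. An unadjusted test uses 1.96.

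**3. Why step-down dominates with three means.** Test the largest difference at the Tukey value; only if it is significant, test each remaining pair at an unadjusted two-sided 5%.
- All three means equal: any false rejection requires the range test to reject, which has probability 5%.
- Exactly one pair equal: only that pair can be falsely rejected, and it must pass a 5% test.
- Any Tukey rejection means that the range test has rejected and that the pair exceeds 2.35, hence also 1.96. No Tukey rejection can be lost.

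**4. Type I error by simulation** (1,000,000 runs for the Tukey and step-down error grid, 196 per arm).
- All means equal, family-wise: Tukey 0.050, step-down 0.050, Bonferroni 0.044, Scheffé 0.038. Per comparison: Tukey 0.0191, Bonferroni 0.0167, Scheffé 0.0144.
- One arm far from the other two, error on the remaining null pair: Tukey 0.019, step-down rising to a maximum of 0.050.

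**5. Power by simulation** (400,000 runs per setting; step-down lost no Tukey rejection in any of them). The value d = 0.231 gives 80% power for an unadjusted two-arm test at 294 per group: (1.960 + 0.842) × √(2/294) = 0.231. The value d = 0.459 is the two-group equivalent of 5% variance explained: 2 × √0.0526 = 0.459.

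| Setting | Contrast | Tukey | Step-down |
|---|---|---|---|
| 390/393/393, d = 0.20, SG equals control | PBI v control | 67.5% | 74.5% |
| 294 per arm, d = 0.231, SG equals control | PBI v control | 67.5% | 74.5% |
| 294 per arm, d = 0.231, SG midway | PBI v control | 67.5% | 69.3% |
| 294 per arm, d = 0.231, SG midway | each smaller contrast | 17% | 27% |
| 196 per arm, d = 0.459, SG equals control | PBI v control | 98.6% | 99.4% |
| 177 per arm, d = 0.459, SG equals control | PBI v control | 97.5% | 98.8% |
| 196 per arm, d = 0.459, SG midway | each smaller contrast | 46.8% | 62.0% |
| 177 per arm, d = 0.459, SG midway | each smaller contrast | 42.4% | 57.6% |

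The first two rows agree because both have nearly the same noncentrality: 0.20/√(1/390 + 1/393) and 0.231/√(2/294) are both 2.80. The second is therefore not independent support for the first.

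**6. The omnibus-F version.** If the range test is replaced by an omnibus F test at 5%, dominance fails. With SG midway (294 per arm, d = 0.231), Tukey rejects PBI against control and the F-protected test does not in about 1.4% of samples.

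**The case against.** The best defence is that Tukey is a standard procedure, valid at 5% family-wise, with simultaneous intervals that match its decisions. The sentence also refers to varying sample sizes, and its source cannot be checked here, so the methods it was meant to be compared with are unknown. The defence of validity stands. It does not rescue the sentence, which is an unqualified superlative. With unequal arms (150/196/242, d = 0.20, SG equal to control), step-down still holds about 5% and raises PBI-against-control power from 33.7% to 40.0%.

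Second, part of the gain is bought by letting error on a single remaining null pair rise from 1.9% to 5%. That is true, and it stays within the family-wise limit.

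Third, the values of d are illustrative. This stands and limits the point. On the variance-explained reading, PBI against control has about 98% power under Tukey at 177-196 per arm, so little is recovered there.

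Fourth, the section is written in the past tense and enrolment is reported. Replacing the test with one that rejects more often, after outcomes have been seen, would be a post hoc change. This stands and shapes the fix.

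A reader might infer that Tukey costs 29% more dyads per arm. That figure, ((2.344 + 0.842)/(1.960 + 0.842))² = 1.29, compares Tukey with a single unadjusted test. Against step-down at d = 0.231, 80% power needs about 381 per arm with Tukey, about 331 with step-down if SG equals another arm, and about 370 if SG is midway: 381/331 = 1.15 and 381/370 = 1.03, so roughly 3-15%.

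**Conclusion.** The point holds as a false justification with an avoidable loss of power. The dominance of step-down over Tukey for three means does not depend on the effect size or on the assumed 5% level; the size of the gain does. It is 7 points for PBI against control at the illustrative differences if SG equals control, and under 2 points if SG is midway. On the variance-explained reading it is about 1.4 points or less for that contrast. The larger and more consistent gain is on the smaller contrasts when SG lies midway: about 10 points at d = 0.231 and about 15 at d = 0.459.

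A reader might infer that the analysis is invalid, or that the trial is underpowered because Tukey was used. The documents support neither. Tukey controls family-wise error for the three contrasts, and on the variance-explained reading the claim of more than 0.80 survives Tukey adjustment for PBI against control. Power for the smaller contrasts cannot be judged from the plan, which gives neither an expected SG effect nor an effect size as a mean difference.

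**What to change.** - Delete the sentence claiming the most power and least Type I error. State the alpha, the sidedness and the family of tests.
- For each outcome and time point, specify the range step-down test: largest of the three differences at the three-group Tukey value and, only if significant, each remaining pair at an unadjusted two-sided 5%. Do not substitute the omnibus F, which can lose Tukey rejections.
- Keep Tukey simultaneous intervals for reporting.
- If outcomes have already been analysed, keep Tukey as the stated analysis and report step-down beside it as a labelled sensitivity analysis.
- Restate the power paragraph for the three-arm pairwise test actually used, with three-arm group sizes and a named effect metric. This is needed whichever test is kept.

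The cost is one paragraph of the analysis plan and a revised power paragraph, with no new data. The downsides are that step-down decisions have no exactly matching simultaneous intervals, so an interval and a decision may occasionally disagree, and that a single remaining null pair is tested at up to 5% instead of 1.9%.
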